Appendix 4 : French International Index of Erectile Function (IIEF-15)

SCORE HEF5

Ce questionnaire permet d'évaluer votre fonction sexuelle au court des 6 derniers mois :

Au cours des six derniers mois :

- I. A quel point étiez-vous sûr de pouvoir avoir une érection et de la maintenir ?
 - Pas sûr du tout
 - Pas très sûr
 - 3. Moyennement sûr
 - 4. Sûr
 - Très sûr
- II. Lorsque vous avez eu des érections à la suite de stimulations sexuelles, avec quelle fréquence votre pénis a-t-il été suffisamment rigide (dur) pour permettre la pénétration ?
 - 0. Je n'ai pas été stimulé sexuellement
 - 1. Presque jamais ou jamais
 - 2. Rarement (beaucoup moins que la moitié du temps)
 - 3. Quelquefois (environ la moitié du temps)
 - 4. La plupart du temps (beaucoup plus que la moitié du temps)
 - 5. Presque tout le temps ou tout le temps
- III. Lorsque vous avez essayé d'avoir des rapports sexuels, avec quelle fréquence avez-vous pu rester en érection après avoir pénétré votre partenaire ?
 - 0. Je n'ai pas essayé d'avoir de rapports sexuels
 - 1. Presque jamais ou jamais
 - 2. Rarement (beaucoup moins que la moitié du temps)
 - 3. Quelquefois (environ la moitié du temps)
 - 4. La plupart du temps (beaucoup plus que la moitié du temps)
 - 5. Presque tout le temps ou tout le temps
- IV. Pendant vos rapports sexuels, à quel point vous a-t-il été difficile de rester en érection jusqu'à la fin de ces rapports ?
 - 0. Je n'ai pas essayé d'avoir de rapports sexuels
 - 1. Extrêmement difficile
 - Très difficile
 - 3. Difficile
 - 4. Un peu difficile
 - Pas difficile
- V. Lorsque vous avez essayé d'avoir des rapports sexuels, avec quelle fréquence en avez-vous été satisfait?
 - 0. Je n'ai pas essayé d'avoir de rapports sexuels
 - 1. Presque jamais ou jamais
 - 2. Rarement (beaucoup moins que la moitié du temps)
 - 3. Quelquefois (environ la moitié du temps)
 - 4. La plupart du temps (beaucoup plus que la moitié du temps)
 - 5. Presque tout le temps ou tout le temps

Interprétation::

Trouble de l'érection sévère (score de 5 à 10), modéré (11 à 15), léger (16 à 20), fonction érectile normale (21 à 25) et non interprétable (1 à 4).

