• The time to complete recovery and to return to normal professional activities

- Recovery after surgery (Quality of Recovery visual analogue score (QoR VAS)) at 1, 2, 3 and 4 months after surgical procedure;
- Time before returning to professional activities.

• Sexual side effects,

• Sexual quality of life evolution between inclusion, 4 months and 12 months after surgical procedure (IIEF15, Male Sexual Health Questionnaire for Ejaculatory Dysfunction (MSHQ-EjD).

Associated complications,

• Clavien Dindo classification of adverse events at 4 months after surgical procedure.

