11.2.4. SECONDARY CRITERIA

The following analyses will be performed for each cohort, according to the matched treatment group:

- An estimation of the total hospital cost of each surgery procedure based on a top down micro-costing method performed during hospitalization stay;
- A description of the overall and specific urogenital healthcare consumptions during the 3 years of follow-up;
- A description of BPH re-treatment over the 3 years of follow-up (number of patients with a new BPH medication, number of patients hospitalized for BPH surgical procedure);
- A description of urinary symptoms (value of the IPSS, ISI, ICIQ-UI SF scores during the 1st year of follow-up and number of patients with hospitalization for urinary infection, for urinary retention, or for urethral stricture during the 3 years of follow-up);
- A description of the quality of life during the 1st year of follow-up using the IPSS-Q8 score, the Jenkins sleep questionnaire, the EQ-5D-5L questionnaire;
- A description of the recovery after surgery using the Quality of Recovery visual analogue score and the time before returning to normal professional activities;
- A description of the sexual side effects during the 1st year of follow-up using the IIEF15 and MSHQ-EjD questionnaire;
- A description of the associated complications (number and types).

[figure not shown]
A detailed analysis plan will be defined and will be validated by the steering committee of the study. Subsequent modifications must be made before the blinding is lifted on the database and will be systematically validated by the Scientific Council.

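### The IIEF15 named as a sexual-function instrument is appended as a five-item form with six-month recall; if that form is used, its month-4 answers span surgery

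*Protocol*

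**What the plan says.** Section 3.2 sets the sexual endpoint as "Sexual quality of life evolution between inclusion, 4 months and 12 months after surgical procedure", measured by the IIEF15 and the MSHQ-EjD. The IIEF15 is named again in the footnote to the assessment table (9.2), at the inclusion visit (9.3.2) and at visits 4 and 5 (9.6, 9.7). Section 11.2.4 plans "A description of the sexual side effects during the 1st year of follow-up using the IIEF15 and MSHQ-EjD questionnaire". Section 2.2 lists sexual side effects at 4 months and 1 year among the outcomes to be compared between procedures, and section 11.2.1 provides adjusted linear regression for quantitative variables.

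The form is headed "Appendix 4 : French International Index of Erectile Function (IIEF-15"). It prints questions I to V only. Its reference is to "Development and evaluation of an abridged, 5-item version of the International Index of Erectile Function (IIEF-15"). Its grading covers erectile function alone, and the bands end with "fonction érectile normale (21 à 25) et non interprétable (1 à 4"). The recall instruction is "votre fonction sexuelle au court des 6 derniers mois".

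Appendix 5 (MSHQ-EjD) asks about the last month. It has three function items, one bother item and a single line for a total, with no scoring rule.

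**The concern.** There are two difficulties with the IIEF. First, the body of the protocol and its appendix describe different instruments under one name, so a reader cannot tell which questionnaire yields the endpoint. A SAP can define scoring, but it cannot supply questions that were never asked.

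Second, a six-month recall does not fit a visit four months after surgery. The man is asked to summarise a period that begins before his operation. If he does so as instructed, the month-4 value mixes pre-operative and post-operative function, and the change from inclusion is pulled towards zero in both cohorts. A real difference between PUL and TURP/laser would be harder to see at that visit. Fewer sexual side effects are among the benefits hoped for from PUL (1.4, 1.5).

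**Working it through.** **1. Is the appended form a cut-down print of a longer one?** The printed answers are 1 to 5 for item I and 0 to 5 for items II to V.
- Minimum: 1 + 4 × 0 = 1.
- Maximum: 5 + 4 × 5 = 25.
- Printed bands: 1–4, 5–10, 11–15, 16–20, 21–25, which together cover exactly 1 to 25.

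The five items reproduce the form's own grading in full, and the reference under the form is to the five-item version. This is a complete five-item score, not a 15-item form that lost pages in text extraction.

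**2. How much of the recall precedes surgery?** Inputs: recall of 6 months (Appendix 4); visit 4 at month 4 ± 7 days (9.6); visit 5 at month 12 ± 14 days (9.7). With one month = 365.25/12 days, 6 months = 182.6 days and 4 months = 121.75 days.

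Pre-operative days = recall − days since surgery; share = pre-operative days / recall.

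| Visit 4 timing | Pre-operative days | Share |
|---|---|---|
| 7 days early | 182.6 − 114.75 = 67.9 | 37% |
| on time | 182.6 − 121.75 = 60.9 | 33% |
| 7 days late | 182.6 − 128.75 = 53.9 | 30% |

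Taking 6 months as 180 days gives 65.2, 58.2 and 51.2 days (36%, 32%, 28%).

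At month 12 the recall starts at 365.25 − 182.6 = 182.6 days after surgery, or 168.6 to 196.6 days over ± 14 days. None of it is pre-operative.

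**3. Overlap with the baseline recall.** Inclusion is 1 to 90 days before surgery (9.3.2). The baseline recall ends on the inclusion day, and the on-time month-4 recall reaches back 60.9 days before surgery. Overlap = max(0, 60.9 − days from inclusion to surgery):
- 1 day: 59.9 days
- 30 days: 30.9 days
- 60 days: 0.9 days
- 90 days: none

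For men included within about 60 days of surgery, the change score partly compares a period with itself.

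**4. What this does to the month-4 change.** Let w be the weight a man gives to the pre-operative part. If function changes at surgery and is stable on either side of it, the observed change is (1 − w) times the true change.
- Even averaging, on-time visit: w = 0.33, so 67% of the change is seen (63% to 70% over the visit window).
- A man who reports only recent weeks: w = 0, so nothing is lost.

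The documents do not say which is closer.

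**5. The other appended forms.** The IPSS and MSHQ-EjD ask about the last month, the Jenkins scale about 30 days and the ICIQ-UI SF about four weeks. All of these lie after surgery at month 4. Among the appended forms that state a recall period over time, only the IIEF form reaches back before surgery.

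**6. MSHQ-EjD total (minor).** Items 1 to 3 run 1–5, 0–5 and 0–5, higher being better: function 1 to 15. Item 4 runs 0–5, higher being more bothered: literal total 1 to 20. A total of 15 can be full function with no problem (15 + 0) or function 10 with extreme bother (10 + 5). At worst function, extreme bother gives 1 + 5 = 6, while not being bothered at all gives 1 + 1 = 2.

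**The case against.** **The appendix may be a clerical slip.** The citation under the form pairs an abridged five-item version with the label IIEF-15, which looks like a careless rename. Appendix references are loose elsewhere: sections 3.2 and 4.2 place the EQ-5D-5L in appendix 2, which holds the IPSS. If patients receive a 15-item form, the six-month recall may not apply, because the protocol does not give that form's recall period. This stands, and it is why the recall point is conditional. The mismatch itself still needs correcting.

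**A reader might infer that the sexual-function forms fail to measure the endpoint.** The documents do not support that. The recall problem touches one instrument at one of two follow-up visits. The specific sexual benefit claimed in section 1.5 is preserved ejaculation, which the MSHQ-EjD covers with a one-month recall.

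**A reader might take a one-third loss of effect as established.** Only the one-third share of the window is established; the loss needs even averaging.

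**A reader might infer that promised domain scores are lost.** Sections 3.2 and 11.2.4 promise none.

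**A reader might treat the MSHQ-EjD total as a faulty endpoint.** No endpoint or analysis text uses it. The four items are answered separately, so the SAP can score function and bother apart without changing the form. The largest distortion, a best-to-worst contrast of 15 − 6 = 9 instead of 15 − 1 = 14, needs extreme bother at worst function. With a man who is not bothered at all, the contrast is 15 − 2 = 13.

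**Changing forms now could do harm.** Inclusion was planned for Q2 2021 to Q2 2023 and version 6.0 is dated January 2023, so on that calendar most baselines are already collected. A new recall period for men already enrolled would break comparability with their inclusion answers. This stands and shapes the fix.

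**Conclusion.** The protocol contradicts itself: it names the IIEF15 and appends a complete five-item form under that name. This rests on the text alone.

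If the appended form is the one administered, about one third of the month-4 recall (30% to 37% over the visit window) precedes surgery, and it overlaps the baseline recall for men included within about 60 days of their operation. The month-4 IIEF cannot then be read as post-operative function. The direction of the bias is towards no change. Its size runs from nil to about one third or slightly more, depending on how men average over six months.

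Month-12 IIEF and all MSHQ-EjD answers refer to post-operative time. The matter concerns a secondary outcome; the primary outcome and study size are not affected.

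**What to change.** 1. State which form patients complete. If it is the 15-item form, put it in Appendix 4. If it is the printed form, rename the instrument IIEF-5 in sections 3.2, 9.2, 9.3.2, 9.6, 9.7 and 11.2.4.
2. If the printed six-month form has been used, label the month-4 IIEF as spanning surgery and base the erectile-function comparison on month 12. Do not change the recall period for men already enrolled.
3. For any form not yet in use, choose a recall period wholly after surgery at month 4. The earliest permitted visit is about 115 days after surgery, so any shorter recall qualifies, including the one-month recall of the neighbouring forms.
4. Do not use the printed MSHQ-EjD total as a score. Report items 1 to 3 as function and item 4 as bother.

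The cost is a corrected appendix or name, passed to the ethics committee under the protocol's procedure for changes, and a few lines of scoring and labelling in the SAP. No data already collected are lost. The price is a weaker month-4 statement on erectile function.

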Appendix 5: French Male Sexual Health Questionnaire - Ejaculatory Dysfunction (MSHQ-EjD)

Nom:	Prénom :	Date :

Male Sexual Health Questionnaire for Ejaculatory Dysfonction (MSHQ-EjD)

Ces questions sont en rapport avec vos éjaculations au cours du dernier mois

Avec quelle	Tout le	Le plus	Une fois sur	Moins d'une	Jamais /	
fréquence avez-	temps (5)	souvent (4)	deux (3)	fois sur deux	Absence	
vous été capable	5 6 5	2.5		(2)	d'éjaculation (1)	
d'éjaculer au						
cours de vos						
rapports sexuels?						
Comment	Toujours	Un peu	Plutôt	Moins forte	Beaucoup	Ne peut pas
considérez-vous	aussi forte	moins	moins	qu'avant (2)	moins forte	éjaculer (0)
la force de votre	(5)	forte	forte		qu'avant (1)	
éjaculation ?		qu'avant	qu'avant			
		(4)	(3)			
Comment	Toujours	Un peu	Plutôt	Moins	Beaucoup	Ne peut pas
évaluez-vous la	autant (5)	moins	moins	qu'avant (2)	moins	éjaculer (0)
quantité de	2.8	qu'avant	qu'avant	18 18	qu'avant (1)	1776
sperme lorsque		(4)	(3)			
vous éjaculez						
Si vous avez eu	Pas de	Pas du	Un peu	Modéréme	Très gêné (4)	Extrêmement
des difficultés ou	problème	tout gêné	gêné (2)	nt gêné (3)		gêné (5)
n'avez pas réussi	avec mes	(1)		2000		/** × ** *
à éjaculer, en	éjaculations	33 54				
avez-vous été	(0)					
gêné ?						

Total :

Appendix 6: French Quality of Recovery – Visual Analog Scale (QoR-VAS)

Nom:	Prénom :	Date :
Qualité de récu	pération : Échelle visuelle ar	nalogique
Instructions : pour évaluer la quali une croix sur la ligne.	té de votre récupération après la	a chirurgie, veuillez placer
Par exemple, si vous avez très bier	n récupéré, placez votre croix con	mme ceci :
		-x-
Si votre récupération est mauvaise	ဥ, placer la croix comme ceci :	
X		
Veuillez placer votre croix :		
Mauvaise récupération		Récupération excellente
Par ex. : douleurs importantes,		ex. : aucune douleur,
Par ex. : douleurs importantes, mobilisation impossible		ex. : aucune douleur, ise d'une activité normale

Appendix 7 : French EQ-5D-5L (EuroQol Group) questionnaire

Pour chaque rubrique, veuillez cocher UNE case, celle qui décrit le mieux votre santé AUJOURD'HUI. MOBILITÉ Je n'ai aucun problème pour me déplacer à pied J'ai des problèmes légers pour me déplacer à pied J'ai des problèmes modérés pour me déplacer à pied J'ai des problèmes sévères pour me déplacer à pied Je suis incapable de me déplacer à pied AUTONOMIE DE LA PERSONNE Je n'ai aucun problème pour me laver ou m'habiller tout(e) seul(e) J'ai des problèmes légers pour me laver ou m'habiller tout(e) seul(e) J'ai des problèmes modérés pour me laver ou m'habiller tout(e) seul(e) J'ai des problèmes sévères pour me laver ou m'habiller tout(e) seul(e) Je suis incapable de me laver ou de m'habiller tout(e) seul(e) ACTIVITÉS COURANTES (p. ex., travail, études, travaux domestiques, activités familiales ou loisirs) Je n'ai aucun problème pour accomplir mes activités courantes J'ai des problèmes légers pour accomplir mes activités courantes J'ai des problèmes modérés pour accomplir mes activités courantes J'ai des problèmes sévères pour accomplir mes activités courantes Je suis incapable d'accomplir mes activités courantes DOULEURS / GÊNE Je n'ai ni douleur ni géne J'ai des douleurs ou une gêne légère(s) J'ai des douleurs ou une gêne modérée(s) J'ai des douleurs ou une gêne sévère(s) J'ai des douleurs ou une gêne extrême(s) ANXIÉTÉ / DÉPRESSION Je ne suis ni anxieux(se) ni déprimé(e) Je suis légèrement anxieux(se) ou déprimé(e) Je suis modérément anxieux(se) ou déprimé(e) Je suis sévèrement anxieux(se) ou déprimé(e) Je suis extrêmement anxieux(se) ou déprimé(e)

France (French) © 2010 EuroQol Group EQ-5D™ is a trade mark of the EuroQol Group

Appendix 8: French traduction of Jenkins Sleep Evaluation Questionnaire

Nom:	Prénom :	Date:

Jenkins Sleep Evaluation Questionnaire

Parmi les 30 derniers jours, vous est-il arrivé :	Jamais	1 à 3 jours	4 à 7 jours	8 à 14 jours	15 à 21 jours	22 à 30 jours
D'avoir du mal à vous endormir	0	1	2	3	4	5
De vous réveiller quelques fois dans la nuit sans avoir de problème à vous rendormir	0	1	2	3	4	5
De vous réveiller une ou plusieurs fois dans la nuit (y compris vous réveiller trop tôt), et avoir du mal à vous rendormir	0	1	2	3	4	5
De vous réveiller après votre durée de sommeil habituelle en étant fatigué ou épuisé	0	1	2	3	4	5

CIQ-UI SF)	rision of international Consultation on I	ncontinence Questionnaire-Urinary Incontin	nence Sh
Numéro	ICIQ-UI Short Form (Fr	J J M M M A A Date	
personnes ont		n temps. Nous essayons de savoir combien les ne. Veuillez répondre aux questions suivantes, RE DERNIERES SEMAINES.	
1 Votre date	e de naissance:	JOUR MOIS ANNÉE	
2 Sexe (coc	hez la réponse):	Femme Homme	
3 A quelle fr	équence avez-vous des pertes d'urine?	(ne cochez qu'une seule réponse) jamais environ une fois par semaine deux à trois fois par semaine environ une fois par jour plusieurs fois par jour tout le temps 0 1 2 4 tout le temps 5	
	la quantité habituelle de vos pertes d'urir	pertes d'urine, selon votre estimation . ne (avec ou sans protection)?	
	la quantité habituelle de vos pertes d'urin z qu'une seule réponse)		
(Ne coche	e générale, à quel point vos pertes d'urine? Entourez un chiffre entre 0 (pas du tout) et 0 1 2 3 4 5 6 7 tout	nulle 0 une petite quantité 2 a moderate amount 4 a large amount 6 e vous dérangent-elles dans votre vie de	
5 De manière tous les jours	e générale, à quel point vos pertes d'urine? Entourez un chiffre entre 0 (pas du tout) et 0 1 2 3 4 5 6 7 tout	nulle une petite quantité a moderate amount a large amount 6 e vous dérangent-elles dans votre vie de 10 (vraiment beaucoup) 8 9 10 Vraiment beaucoup : ajoutez les scores 3+4+5	

Merci d'avoir pris le temps de répondre à ces questions.

Copyright © "ICIQ Group"
